### Patient Assessment

Patients will be assessed during surgery and in the postoperative period while in the hospital. After discharge, patients will be followed routinely to ensure complete bony consolidation of the fracture and at 4 to 12 weeks postoperatively. The primary

outcome variable is application time for placement of arch bars. Secondary outcomes include intra-operative surgical time length of stay after surgical procedure, length of stay, hospital charges, fracture healing and complications.

All data will be collected by the PI or CI during the initial admission for surgery to repair the fracture or at the one week and 6 week follow-up appointments. All data will be recorded on a standard data collection sheet. Subjects will have not have any questionnaires or surveys to complete. Demographic, preoperative, operative and postoperative variables will be recorded and analyzed. Demographic data includes age, sex and race. Preoperative variables include medical history (DM and HIV), social history, fracture location, number of fractures, time from injury to surgery and antibiotic use. Operative variables include time for arch bar application, surgical time and surgical approach. Post operative variables include fracture healing, follow-up, complications and hospital charges. It is anticipated that the study will conclude at 24 months. All subjects will be paid \$50 at the 4 to 12 week follow-up visit.

### Data Collection

A data collection sheet will be used to record demographic, preoperative, operative and postoperative variables. A separate copy of the data collection sheet is attached. All data collection sheets (unscrubbed and scrubbed) will be kept in a locked office. All data will be entered into a computer and this will be both password protected and secured in a locked office.

### Data Safety Monitoring Plan

[figure not shown]
The use of either Erich arch bars or Stryker Hybrid arch bars are both FDA approved and used in clinical practice routinely to immobilize the jaws due to fracture. They can immobilize the jaw for 4 to 6 weeks to allowing healing when open surgery is not indicated or wanted by the patient. They can also immobilize the jaw temporarily during surgery to allow the surgical placement of titanium plates and screws to repair the fracture. There are no anticipated risks for subjects recruited to this study. However to ensure safety of subjects the investigators have appointed [name] MD as the medical monitor. The medical monitor responsibilities include

- Pre-investigation discussion to verify understanding of the protocol, DSMB and IRB requirements.
- Ensure that that eligibility and exclusion criteria are adhered to ensure the appropriate risk/benefit ratio for subjects.
- Ensure written consent is obtained for each subject

- Ensure that subjects are 18 yrs of age, non-pregnant and not actively seeking to become pregnant, not breast feeding and are not disadvantaged populations.
- Ensure that data on adverse outcomes is recorded appropriately in the surgical operative report and during the follow-up visits.
- Provision for subject withdrawal and documentation for reasons of discontinuation.
- Ensure that data is entered in real time to provide electronic access on a monthly basis.
- Three Monthly conference with the investigators.
- Review subject records periodically to ensure that data is accurate and legible. Of particular importance will be recognizing any data omission, missing visits or examinations, drop-out subjects and reasons for withdrawal and satisfactory completion of informed consent.
- A written record of the teleconference and any site visits will be kept as well as any corrective action recommended by the monitor.

## Budget

### 1) Research Coordinator 0.3 FTE

- Prepare and submit IRB application
- Follow subjects and ensure adequate F/U
- Data entry
- Record Data on site
- Issue Reimbursement to subjects

30% of 1 FTE (\$46000) for 2 yrs  
plus fringe 26.5% \$34,914

2) Subject Reimbursement (100)		\$5000
3) Redcap data base (electronic)		
• Setup		
• Annual fees		\$2500
4) Data analysis and randomization		\$3000
5) Salary Support		
• [name] [name]	1% effort	\$5000
6) Indirect	39%	\$19661
TOTAL		\$70075

Statistical Analysis

NCT02283528

Unique Protocol ID:
IRB00076048

A Comparison of Stryker Hybrid Arch Bars Versus Erich Arch Bars for Maxillomandibular Fixation of Mandibular Fractures: A Prospective Randomized Study

Principal Investigator
[name] [name], MDSc, FRACDS, FRACDS

November 23, 2018

A data collection sheet was used to record demographic, preoperative, operative and postoperative variables. Preoperative and operative variables were compared between the treatment groups using t-tests for age, and a combination of χ^2 and Fisher's exact tests for other variables. Arch-bar application times were compared among the preoperative and operative variables using Pearson correlation for age and a combination of t-tests and one-way ANOVA. Treatment groups versus time of arch-bar application and length of surgery were tested using t-tests. Multiple regression was used after covariates were determined using stepwise linear regression. All analysis was performed using the patients' original treatment assignment (intent-to-treat). All results were considered statistically significant if the p-values were less than 0.05.

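### Among covariates the SAP gives a continuous-variable method to age alone, and it relates covariates to application time without the arm; both cost precision in the covariate screen

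*SAP*

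**What the plan says.** The SAP is a single paragraph. For the comparison of arms, preoperative and operative variables are "compared between the treatment groups using t-tests for age, and a combination of" χ² and "Fisher's exact tests for other variables". For the relation of application time to the same variables, it works "using Pearson correlation for age and a combination of t-tests and one-way ANOVA". So age is the only covariate given a method for continuous data, and the second comparison mentions no arm term.

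The Protocol, under Patient Assessment, lists among the preoperative variables "fracture location, number of fractures, time from injury to surgery and antibiotic use". One of these is a duration and one is a count. Its operative list reads: "Operative variables include time for arch bar application, surgical time and surgical approach".

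The arm does appear elsewhere in the SAP: "Treatment groups versus time of arch-bar application and length of surgery were tested using t-tests". A modelling step is also described: "Multiple regression was used after covariates were determined using stepwise linear regression". The SAP does not say how covariates are coded in that regression or whether the arm is kept in it. The significance rule is "All results were considered statistically significant if the p-values were less than 0.05", with sidedness not stated.

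**The concern.** A duration cannot be entered in a χ² or Fisher test, or serve as the grouping factor of a t-test or ANOVA, unless it is first cut into groups. Grouping discards the information within each group and makes the answer depend on where the cuts fall. A count such as number of fractures can be used as its own groups, but these tests ignore the fact that three fractures are more than two.

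The arm matters for a different reason. The Schema names arch-bar type as the primary predictor, and the Introduction says the hybrid bar may shorten placement. If it does, a covariate comparison without the arm leaves that difference in the residual variation and so blurs the covariate's own effect.

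What is at stake is whether real determinants of application time are seen in the screen and, if the screen or its coding carries over, how well the adjusted model explains application time.

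**Working it through.** **Inputs from the documents.** Sample size: 40 CR + 60 ORIF = 100 (Protocol, Sample size). Allocation is 1:1 within each stratum, 20 + 20 and 30 + 30 (Protocol, Therapy). The threshold is 0.05 (SAP). Application time is recorded at surgery, so all 100 are used here despite the 30% dropout allowance.

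**Inputs assumed.** Two-sided testing, the covariate's correlation with application time, its distribution, and the arm effect d in within-arm SD units. The Protocol says that no prior studies guide the sample size and gives no effect size, SD or power. There is therefore no power figure in the plan to reproduce.

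**Step 1: information kept after grouping.** For a covariate cut into k equal groups, the share of linear-trend information kept is the between-group variance divided by the total variance.
- Normal covariate: 64% (k = 2, which is 2/π), 79% (k = 3), 86% (k = 4).
- Right-skewed covariate (lognormal, log-SD 0.8), effect linear in raw units: 37%, 51%, 60%.

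**Step 2: power, normal covariate, correlation 0.25, n = 100.** Approximate power is Φ(atanh(r)·√97 − 1.96).
- Continuous: atanh(0.25) = 0.2554; 0.2554 × 9.849 = 2.515; Φ(0.555) = 71%.
- Median split: r = 0.25 × √0.637 = 0.1995; atanh = 0.2022; 0.2022 × 9.849 = 1.991; Φ(0.031) = 51%.

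Simulation gives about 72% and 53%, in agreement to within two points.

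**Step 3: leaving out the arm.** With 1:1 allocation the pooled variance is SD²(1 + d²/4), so the information kept is 1/(1 + d²/4), and a within-arm correlation of 0.30 shrinks to 0.30/√(1 + d²/4).

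| d | Information kept | Correlation ignoring arm | Power ignoring arm: formula | Power ignoring arm: simulation | Power with arm: simulation |
|---|---|---|---|---|---|
| 0 | 100% | 0.300 | 86% | 87% | 87% |
| 0.5 | 94% | 0.291 | 84% | 83% | 85% |
| 1 | 80% | 0.268 | 77% | 78% | 87% |
| 1.5 | 64% | 0.240 | 67% | 67% | 86% |

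The true power with the arm does not depend on d. Its variation down the last column is simulation noise; the formula, with one more degree of freedom spent, gives 86%.

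**Step 4: both together.** The losses multiply. A median split of a normal covariate with d = 1 keeps 0.64 × 0.80 = 51%. In simulation at correlation 0.30 and d = 1, power is about 59% (split, no arm), 68% (split, arm), 78% (continuous, no arm) and 86% (continuous, arm).

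**Step 5: the skewed case.** With the lognormal covariate, correlation 0.25 and an effect linear in raw days, power is about 67% on raw days, 55% on log-days and 32% after a median split. If the effect is instead linear in log-days, it is about 72% on log-days and 52% after a split. The drop from 67% to 32% therefore describes raw days only and is not the gain from a log transform.

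**The case against.** The strongest reply is that a one-paragraph SAP is a summary, so its list of tests is weak evidence of how any unnamed variable was handled. Surgical time illustrates this. The Protocol lists it as an operative variable, which read literally would send it to a categorical test between arms, yet the SAP tests length of surgery by arm with a t-test. The data collection sheet is a separate attachment and was not available, so time from injury to surgery may have been recorded in preset categories. All this stands as a caution about what was done. It does not supply the missing coding.

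Several stronger readings are tempting and are not supported:
- A reader might infer that age is the only quantity treated as continuous. Application time and length of surgery are also analysed as continuous, so the statement holds for covariates only.
- A reader might infer that number of fractures must be cut. It is a small count whose observed values can be the groups. It loses order, and the power figures above do not measure that loss.
- A reader might infer that cut-points were chosen after looking at the data. The documents mention no cut-points at all.
- A reader might infer that a degraded variable, or no arm term, enters the multiple regression. The SAP is silent on both, and silence is not exclusion.
- A reader might infer that the arm is the strongest determinant of application time. The Introduction says only that the hybrid bar could reduce it, and nothing ranks the arm against stratum, surgeon or fracture pattern.

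It is also fair to say that the Protocol's objectives compare the two bars and do not ask what determines application time, so this is a secondary matter.

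**Conclusion.** The point holds in limited form. Read as written, the SAP requires time from injury to surgery to be grouped at unstated cut-points, drops the ordering of number of fractures, and relates covariates to application time without the arm. Each choice is less efficient than an alternative available on the same data.

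The size rests wholly on assumed inputs. Grouping takes power from about 72% to 53% for a normal covariate at correlation 0.25. Omitting the arm costs nothing if the arm has no effect, about 2 points at 0.5 SD, 9 at 1 SD and 19 at 1.5 SD, at correlation 0.30.

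The loss is one of precision, in the screen and possibly in the adjusted model. It would be wrong to conclude that the primary result is compromised: the unadjusted t-test by arm does not use these covariates. Nor does omitting the arm bias the effects of baseline covariates, because randomisation makes them unrelated to the arm in expectation. That protection does not extend to variables arising after randomisation, such as surgical time. This is a worthwhile improvement rather than a serious defect.

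**What to change.** - Analyse time from injury to surgery as numeric, in log-days if skewed, and number of fractures as numeric. Compare both between arms with a t-test or a rank test.
- Relate each covariate to application time in a linear model that contains the arm, the ORIF/CR stratum and that covariate. Report the result as minutes per unit with a 95% CI.
- State that the arm is kept in the multiple regression whatever the stepwise procedure selects, and state how each covariate is coded there.

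The cost is a few sentences and a few more model runs on data already specified for collection, provided that time from injury to surgery was recorded as a number. The SAP is dated November 2018 and written in the past tense. If results are already known, the revised analysis should be labelled as a re-analysis and shown beside the original.

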**Schema:**

Consecutive patients presenting to Grady Memorial Hospital with mandibular fractures will be evaluated for recruitment in this pilot study. Patients requiring either open reduction and internal fixation (ORIF) or closed reduction (CR) will be included in the study.

The choice of surgical method (ORIF versus CR) will be determined by the patient preference in conjunction with the attending surgeons expert opinion. The surgical procedure for closed treatment is a simple and standardized procedure involving placement of arch bars and maxillomandibular fixation (MMF) for a period of 4-6 weeks. The surgical procedure for ORIF will involve the placement of arch bars intraoperatively, exposure of fractures by intraoral or transcutaneous incisions, intraoperative MMF and ORIF. All procedures will be done under a general anesthesia. All eligible subjects will be initially stratified to ORIF or CR. Subjects within each group will then be randomized to either Stryker Hybrid arch bars or Erich arch bars (control). In all groups the arch bars will be left in place for six weeks. Stryker Hybrid arch bars will be placed according to the manufacturers instruction using a minimum of four locking screws per arch. Erich arch bars will be placed using a combination of 24 and 25 gauge wire as is the historical technique. Arch bar removal is a simple procedure that will be completed under local anesthesia in the outpatient clinic.

The primary predictor variable is the type of archbar (Stryker Hybrid versus Erich). The primary outcome variable is time required to place the arch bars. Secondary outcomes include union (nonunion, fibrous union, malunion), complications, hospital charges and need for additional procedures

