### Therapy

In the ORIF group, thirty patients will be randomized to each arm of the study (30 Stryker hybrid arch bars and 30 Erich arch bars). In the CR group, twenty subjects will be randomized to each arm of the study (20 Stryker hybrid arch bars and 20 Erich arch bars). A number of different resident surgeons will perform the surgical treatment including the application of MMF. All residents will complete Stryker clinical skills training and will be standardized as the application process and technique for both arch bar systems. For all study subjects, time will be recorded from start to completion of maxillary and mandibular arch bar placement, and from insertion of throat pack to removal of throat pack. This will be measured using two different electronic timers to record the respective times. All arch bars will be left in place (ORIF and CR) for a period of 6 weeks. Patients will be discharged from the hospital as soon as possible after medically stable from surgery. Patients will be seen for follow up routinely for a minimum of 6 weeks postoperatively to ensure appropriate healing.

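### The ORIF/CR randomisation stratum is not fixed in the analysis of application time or length of surgery; read as pooled, the t-tests are conservative and can lose power, mainly for length of surgery.

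*SAP*

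**What the plan says.** The protocol's Schema sets the design: "All eligible subjects will be initially stratified to ORIF or CR", with bar type randomised inside each of the two groups. The Therapy section gives the numbers. For ORIF, "thirty patients will be randomized to each arm of the study"; for CR the figure is twenty per arm.

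The same section defines two timed outcomes. Application time, the primary outcome, covers placement of the upper and lower bars only. Surgical time, a secondary outcome, runs "from insertion of throat pack to removal of throat pack".

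The SAP is one paragraph. On the arm comparison it says "Treatment groups versus time of arch-bar application and length of surgery were tested using t-tests". On adjustment it says "Multiple regression was used after covariates were determined using stepwise linear regression". It never names ORIF/CR, and it does not say whether the t-tests pool the strata or are run within each. It also leaves open which outcome was regressed, which covariates were candidates, whether treatment was kept in the model, and which analysis is the main one.

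One protocol sentence bears on the candidate list. Patient Assessment states "Operative variables include time for arch bar application, surgical time and surgical approach".

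**The concern.** Stratifying the randomisation balances the stratum between arms, so an ORIF-CR difference adds nothing to the true variance of the treatment difference. A pooled t-test does not use this. It leaves the between-stratum spread in the residual variance and reports a standard error that is too large. Confidence intervals are then too wide, and a real difference may be missed.

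The two outcomes are not equally exposed. Length of surgery includes fracture exposure and fixation in ORIF but not in CR, so a sizeable gap between strata is plausible. For application time, only bar placement is timed in both strata, and the gap may be small.

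Pooling is an inference, but the natural one. Bar type is the only randomised factor, and the first objective asks a single question across both surgical methods.

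**Working it through.** **Inputs from the documents.** ORIF 30+30 and CR 20+20 (Therapy); significance at p below 0.05 (SAP). The total reproduces: 30+30+20+20 = 100, so 50 per arm with an ORIF share of 0.6 in each arm. The Sample size section gives no effect size, SD or power, so 100 cannot be derived from a power calculation.

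**Assumptions.** D is the ORIF-CR gap in mean time, in within-stratum SDs; it is not in the documents and is varied. Effect sizes are illustrative. Within-stratum SDs are equal, errors are normal, tests are two-sided, and the planned balance is achieved.

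**Step 1: standard error.** With within-stratum SD 1, the true SE of the arm difference is sqrt(2/50) = 0.20. The pooled t-test uses variance 1 + 0.6 × 0.4 × D² = 1 + 0.24D², so its SE is too large by sqrt(1 + 0.24D²).

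**Step 2: type I error.** By formula it is 2Φ(−1.96 × sqrt(1 + 0.24D²)). Simulation used 40,000 trials per setting.

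| D | Variance factor | SE factor | Reported SE | Type I, formula | Simulated: t-test / stratum in model | Mean 95% CI width (SD): t-test / stratum in model |
|---|---|---|---|---|---|---|
| 0.5 | 1.06 | 1.03 | 0.206 | 0.044 | 0.042 / 0.048 | 0.82 / 0.79 |
| 1 | 1.24 | 1.11 | 0.223 | 0.029 | 0.029 / 0.050 | 0.88 / 0.79 |
| 2 | 1.96 | 1.40 | 0.280 | 0.006 | 0.006 / 0.049 | 1.11 / 0.79 |

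In terms of CI width, this equals losing 1 − 1/(1 + 0.24D²) of the sample: 6%, 19% and 49%.

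**Step 3: power.** By formula it is Φ(effect/0.20 − 1.96 × sqrt(1 + 0.24D²)). For an effect of 0.6 SD and D = 2 this is Φ(3.00 − 2.74) = Φ(0.26) = 0.60; simulation gives 0.583. Simulated power, t-test v stratum in the model:

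| Effect (SD) | D = 0.5 | D = 1 | D = 2 |
|---|---|---|---|
| 0.4 | 48 v 51% | 42 v 51% | 22 v 51% |
| 0.6 | 83 v 84% | 78 v 84% | 58 v 84% |
| 0.8 | 97 v 98% | 96 v 98% | 88 v 98% |

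At D = 0 nothing is lost or gained (0.845 v 0.844 at 0.6 SD).

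**Step 4: sensitivity.**

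- *Unequal SDs.* With the ORIF SD 1.5 times the CR SD (effect 0.6 and D in CR SDs), power is 56.5 v 61.6% at D = 1 and 41.9 v 61.1% at D = 2.
- *After 30% drop-out.* This leaves 35 per arm (21 ORIF + 14 CR). Take an effect of 0.67 SD, which the adjusted analysis detects with 80% power. By formula the t-test has 73% at D = 1 and 52% at D = 2.
- *Stepwise selection.* Suppose ORIF/CR was a candidate, treatment stayed in the model, and selection was at p < 0.05. The stratum is then kept in 68%, 99.8% and 100% of trials at D = 0.5, 1 and 2, and power at 0.6 SD returns to about 84%.

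**The case against.** The strongest reply is that the regression may already do the job. The SAP screens application time against preoperative and operative variables, and surgical approach is a recorded operative variable. Where the gap is large enough to matter, stepwise selection would nearly always pick it up; where selection often misses it (D = 0.5), ignoring it costs only 1.4 points at 0.6 SD (83.0 v 84.4%). That is sound if ORIF/CR was a candidate and treatment stayed in, but the SAP states neither. Surgical approach might also mean the incision route. For length of surgery, no covariate screening is described.

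Four further limits stand:

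- **D is unknown.** The protocol supports a direction for length of surgery, not a size. The largest losses come from an assumed D of 2.
- **The sample-loss equivalence holds for CI width, not power.** At D = 2, an adjusted analysis of 51 subjects has power 29%, 56% and 80% at 0.4, 0.6 and 0.8 SD, against 22%, 58% and 88% for the pooled t-test on 100.
- **The tests may have been run within strata.** The figures above would then not apply. The SAP does not say so, and each test would rest on 30 or 20 per arm.
- **Conservatism needs balance within strata.** Registration and Randomization mentions sealed envelopes but no separate sets per stratum. If allocation ignored the stratum, simulation puts type I error at about 0.05. Power at a 0.56 SD effect still falls, to 69% at D = 1 and 50% at D = 2, against about 78% adjusted.

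This is also a pilot with no power target, so none is missed.

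**Conclusion.** The concern holds. The randomisation is stratified by ORIF/CR, and nothing in the SAP makes that stratum part of the analysis of either time outcome. It is a matter of precision and specification, not validity: with the planned balance the treatment estimate is unbiased and the t-test errs on the cautious side. The cost is negligible for a gap up to about 0.5 SD and substantial from about 1 SD, on the pooled reading and with D assumed. It probably matters little for application time and may matter a good deal for length of surgery. It is worth correcting because the remedy is nearly free.

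**What to change.** For each time outcome, specify as the main analysis a linear model with treatment and the ORIF/CR stratum as randomised, both forced in and neither left to stepwise selection. Report the adjusted mean difference with its 95% CI. Within-stratum differences can be given as supportive results. If the stepwise regression is kept, label it secondary and state its outcome and candidate covariates.

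The cost is one residual degree of freedom (98 to 97 with 100 subjects) and no new data. Because the SAP is written in the past tense, this means rerunning existing data, labelled as such, plus a change of wording.

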### Sample size

No prior studies exist to guide sample size calculations. It is anticipated that this pilot study will include a total of 40 subjects in the CR arms and 60 subjects in the ORIF arms. This study will allow for a drop out rate 30% for the outcome variables which is consistent with the patient population based on prior studies.

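### Two analyses of application time, neither named primary: a t-test that ignores the ORIF/CR strata and, apparently, a stepwise-built regression, giving a false-positive rate of about 5% to 8% if either may count

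*SAP*

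**What the plan says.** The protocol's Schema fixes the question: "The primary outcome variable is time required to place the arch bars", and "The primary predictor variable is the type of archbar (Stryker Hybrid versus Erich"). The Schema also fixes the design: "All eligible subjects will be initially stratified to ORIF or CR", with randomisation to bar type inside each group. The Sample size section anticipates "a total of 40 subjects in the CR arms and 60 subjects in the ORIF arms", and the Therapy section splits these 30/30 and 20/20.

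The protocol has no analysis section. The SAP is a single paragraph in the past tense, dated November 23, 2018. On the arm effect it says "Treatment groups versus time of arch-bar application and length of surgery were tested using t-tests" and then "Multiple regression was used after covariates were determined using stepwise linear regression". Just before these sentences it reports outcome-based screening of the other variables: "Arch-bar application times were compared among the preoperative and operative variables using Pearson correlation for age", with t-tests and ANOVA for the rest. It closes with one threshold: "All results were considered statistically significant if the p-values were less than 0.05".

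The SAP does not give the regression's outcome, the candidate covariates, the entry and exit rules, the terms that are always kept (arm, stratum), or which analysis answers Objective 1.

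**The concern.** Two analyses of one primary comparison, each read at 0.05 with no order between them, give two chances of a positive claim. The second model is not known until the outcomes have been seen, because its covariates are picked by their relation to the outcome. The first ignores a factor that the randomisation balanced. If that factor predicts application time, the t-test's standard error is too large and the test loses power.

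What is at stake is the error rate and clarity of the claim for Objective 1. The documents do not exclude operative variables from the candidate pool, and the protocol's Patient Assessment section counts surgical time among these. Surgical time arises after randomisation and should not be adjusted for.

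**Working it through.** **Plan's own figure.** The only error-rate figure is the 0.05 threshold. No effect size, SD or power is given, so there is no sample-size calculation to reproduce.

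**Inputs from the documents.** 100 patients; ORIF 30/30, CR 20/20; p < 0.05, taken as two-sided.

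**Assumptions.** R² is the share of outcome variance explained by stratum and covariates together, taken as 0.3 to 0.5. Let s be the part of that R² carried by the stratum, from 0 to 1. A result counts as positive if either test is significant, and the regression models application time.

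**Ceiling.** Two independent tests: 1 − 0.95² = 9.75%. The two tests share data, so the true figure is lower.

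**Formula.** With exact balance within strata, the stratum adds nothing to the difference between arms, but the t-test still counts its variance in the standard error. Under no effect, approximately:

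- unadjusted statistic: normal, variance 1 − sR²
- adjusted statistic: normal, variance 1
- correlation: √[(1 − R²)/(1 − sR²)]
- t-test alone: 2 × P(Z > 1.96/√(1 − sR²))
- either test: 1 − P(both statistics lie within ±1.96)

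Example with s = 1. At R² = 0.3, 1.96/√0.7 = 2.34, a two-sided tail of 1.9%. At R² = 0.5, 1.96/√0.5 = 2.77, a tail of 0.6%. The correlation is then 1, so the t-test is significant only when the adjusted test is, and the either-test rate is 5.0%.

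| R² | s | Correlation | t-test alone | Either test |
|---|---|---|---|---|
| 0.3 | 0 | 0.837 | 5.0% | 7.6% |
| 0.3 | 0.5 | 0.907 | 3.4% | 6.0% |
| 0.3 | 1 | 1 | 1.9% | 5.0% |
| 0.5 | 0 | 0.707 | 5.0% | 8.3% |
| 0.5 | 0.5 | 0.816 | 2.4% | 5.9% |
| 0.5 | 1 | 1 | 0.6% | 5.0% |

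**Check by simulation, fixed adjusted model.** 20,000 null trials per row with the planned arms gave either-test rates of 7.6%, 6.1% and 5.2% at R² 0.3, and 8.3%, 5.9% and 4.7% at R² 0.5. A separate run of 6,000 trials at R² 0.3 gave 7.7%, 6.7% and 4.9%; its simulation error is about √(0.06 × 0.94/6000) = 0.3 points.

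**With actual stepwise selection.** Stratified arms, 10 candidates, the stratum as one of three equally prognostic variables, arm forced in, entry 0.05 and exit 0.10, 12,000 null trials. The either-test rate was 6.6% at R² 0.3 and 6.8% at R² 0.5. At R² 0.3 it was 7.5% with entry at 0.15, and 7.7% with 70 patients. The stepwise regression alone, with the arm forced in, gave 5.1% to 6.4% across all scenarios run. Most of the excess therefore comes from having two undesignated tests, not from the selection.

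**Only if the arm is itself a stepwise candidate.** It is then reported from the regression only when selected:

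| True effect (SD) | Mean retained estimate | Ratio | Arm dropped |
|---|---|---|---|
| 0.30 | 0.48 | 1.60 | 67% |
| 0.40 | 0.51 | 1.28 | 43% |
| 0.57 | 0.62 | 1.09 | 15% |
| 0.80 | 0.80 | 1.00 | 0.3% |

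The first three rows assume 15 other candidates (800 trials each); the last assumes 10 (3,000 trials). With 10 candidates, a true 0.40 SD gave 0.50 and a drop rate of 36%, so the exact figures move with the assumptions.

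**After the fix.** One fixed model with arm and stratum had a false-positive rate of 4.8% to 5.2% across the same null scenarios.

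**The case against.** The strongest reply is that the paragraph is terse rather than wrong. It says that stepwise determined the covariates and that a regression followed. The Schema gives bar type a separate role as primary predictor, so the ordinary reading keeps the arm in the model. The t-test stands whatever stepwise does. No sentence says that either test may carry the claim, and the regression's outcome is not stated; the sentence before it also covers length of surgery. Stratification makes the t-test conservative when the stratum is prognostic, which offsets the double testing. The study also calls itself a pilot.

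Most of this stands, and it limits the point. A reader might infer that the error rate certainly exceeds 5%. The documents do not support that: with a fully prognostic stratum it stays at about 5%. A reader might also infer that the reported effect is exaggerated by 28% or 60%. That needs the arm in the selection pool, which the text does not say; it can affect only the adjusted coefficient, and it fades as the true effect grows.

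What the reply does not remove is the missing designation. The SAP calls every p below 0.05 significant, pilot or not, and no passage in either document says which analysis answers Objective 1 or that the stratum is kept.

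**Conclusion.** The point holds as a defect of specification with a modest numerical consequence. The either-test false-positive rate runs from about 5% (stratum carries all the prognostic variance) to about 8% (it carries none). This rests on the planned stratified arms, an assumed R² of 0.3 to 0.5, application time as the regression outcome, and either test being allowed to count. At the low end the problem changes form: the t-test runs at about 0.5% to 2% instead of 5% and wastes power.

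Exaggeration of the adjusted estimate is a conditional risk, not a finding. The past tense shows that the SAP text describes completed work. It does not show that the model was chosen to suit the result, and that should not be inferred.

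**What to change.** Name one primary analysis: a linear model for application time with arm and ORIF/CR stratum always included and a short covariate list fixed without reference to outcome, drawn from pre-randomisation variables (for example age and number of fractures). Report the mean difference in minutes with a 95% CI. State that the t-test is supportive and cannot carry a claim by itself. Drop the stepwise model or, if it has already been run, report it as exploratory with its outcome, candidate list and entry and exit rules.

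The cost is SAP wording and one model run. With the example covariates, residual degrees of freedom go from 98 to 95 with 100 patients, and the freedom to choose covariates later is lost. In return the error rate is nominal and power is usually better. In the stratified simulation (R² 0.3, one third of it from the stratum, true effect 0.40 SD), power rose from 50% with the t-test to 55% with arm and stratum alone.
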